3.6 Treatment assignment and treatment groups

Safety, PK, PD and efficacy analyses will be assigned treatment as described in [Section 3.5](#).

Analyses will be performed by treatment group and for all subjects (if applicable) as described in [Section 3.1](#).

The Treatment Groups for Dosing Period 1 will be as follows:

- Placebo
- UCB7665 7mg/kg

For Dosing Period 2 and the Observation Period the following treatment groups will be considered for analysis and will be displayed as such in the TFLs (the first two groups will only be utilized for observation period in case patients do not receive any dosing in period 2):

- Placebo
- UCB7665 7mg/kg
- Placebo - UCB7665 7mg/kg
- Placebo - UCB7665 4mg/kg
- UCB7665 7mg/kg - UCB7665 7mg/kg
- UCB7665 7mg/kg - UCB7665 4mg/kg

These Treatment Groups will be used for all analyses.

3.7 Center pooling strategy

It is planned to recruit subjects in USA, Canada, and Europe in this study, with possible extension to other regions and countries. The data from different sites will be pooled for all analyses.

3.8 Coding dictionaries

All AEs and medical history will be coded for analysis according to the Medical Dictionary for Regulatory Activities (MedDRA)[®] coding dictionary, using the latest version available. Prior and concomitant medications will be coded for analysis using the latest version of the World Health Organization Drug dictionary (WHO-DD). Medical procedures will not be coded.

3.9 Changes to protocol-defined analyses

In protocol section 14.3.2, it is described that the secondary variable change from baseline in at Visit 9 will be analyzed utilizing similarly to the approach used for QMG. However, since MGADL is measured only at Visit 2 and Visit 9, it is not possible to use the repeated measures model and a simpler model will be used, see [Section 8.2.2](#).

4 STATISTICAL/ANALYTICAL ISSUES

4.1 Adjustments for covariates

In the analysis of the efficacy variables, the Baseline value of the QMG, MG-composite score, MGADL score or MGII score will be used as a covariate in the analysis of the respective variable.

4.2 Handling of dropouts or missing data

In general, there will be no imputation of missing data unless stated otherwise below.

4.2.1 Efficacy data

The rules for handling missing data of single items in the calculation of the overall QMG, MGADL or MGII scores at a certain visit are described in [Section 14.1](#), [Section 14.3](#) and [Section 14.5](#), respectively. Missing overall scores at a certain visit will not be imputed.

4.2.2 Safety laboratory data

Measurements below the limit of quantification (BLQ) will be imputed with half of the lower limit of quantification (LLOQ) for the purpose of calculating change from Baseline. Measurements above the limit of quantification (ALQ), if applicable, will be imputed to the upper limit of quantification. These rules will be applied to all safety laboratory data including clinical chemistry and urinalysis.

Descriptive statistics will be calculated if at most 33% of the individual data points at a time point are missing or are either not quantifiable (<LLOQ) or ALQ.

4.2.3 Pharmacodynamic data

Measurements BLQ are not anticipated for the serum total serum IgG data. In the event that any measurements BLQ are received, these will be regarded as missing for the calculation of descriptive statistics and changes from Baseline.

Descriptive statistics will be calculated if at most 33% of the individual data points at a time point are missing or are either not quantifiable (<LLOQ) or ALQ as described in [Section 4.2.2](#).

For the MG-specific autoantibodies and IgG subclasses, measurements BLQ will be imputed with LLOQ/2 for the purpose of calculating change from Baseline. Measurements ALQ, if applicable, will be imputed to the upper quantification limit.

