9.2 Pharmacodynamics

The analysis of the PD data will be performed on the FAS with the exception of the total serum IgG and IgG subclasses results, which will be analyzed on the PD-PPS. All listings will be presented for the SS.

Any values that are BLQ or ALQ will be handled as described in [Section 4.2.2](#).

All analyses described in this section will be performed on the PD-PPS.

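### A total IgG value below the limit of quantification has two rules in the SAP (missing in 4.2.3, half the LLOQ through 9.2), and the missing rule is the weaker one to keep

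*SAP*

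**What the plan says.** Three places in the SAP bear on a BLQ total IgG value.

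- **4.2.3 Pharmacodynamic data** opens with an expectation: "Measurements BLQ are not anticipated for the serum total serum IgG data". It then gives the contingency: if any arrive, "these will be regarded as missing for the calculation of" descriptive statistics and changes from Baseline. For the other pharmacodynamic analytes the same section says: "For the MG-specific autoantibodies and IgG subclasses, measurements BLQ will be imputed with" LLOQ/2, for the purpose of change from Baseline.
- **9.2 Pharmacodynamics** names total IgG ("IgG and IgG subclasses results, which will be analyzed on the PD-PPS") and then says, with no exception: "Any values that are BLQ or ALQ will be handled as described in" Section 4.2.2.
- **4.2.2 Safety laboratory data**, the target of that reference, reads: "Measurements below the limit of quantification (BLQ) will be imputed with half of the lower" limit of quantification, again for change from Baseline.

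SAP 9.2.1 summarises total IgG as absolute values, change, percent change and maximum decrease. SAP 2.2.2.3 adds the minimum value. The effect on total IgG is a secondary objective (SAP 2.1.2).

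**The concern.** A programmer who follows 4.2.3 and one who follows 9.2 would produce different tables from the same data.

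The choice between the rules also matters statistically. The drug lowers IgG, and Exclusion Criterion 8 in the protocol keeps out subjects with total IgG of 6 g/L or less at Screening. A BLQ result would therefore almost certainly be post-dose and among the lowest levels reached. Setting it to missing removes data because of its value, so the subjects left in the mean are not a fair sample of those measured. It can also discard the visit that defines a subject's minimum value and maximum decrease.

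About 42 subjects end up in four treatment sequences, so 42/4 ≈ 10 per group, and one deleted value is about a tenth of a group's data at that visit. The SAP gives no reason for treating total IgG differently from its own subclasses.

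**Working it through.** The SAP states no figure to reproduce on this point, so the check is a comparison of the rules followed by an illustration of their effect.

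**1. The rules side by side for one BLQ total IgG value**

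| Summary | 4.2.3 | 9.2 via 4.2.2 |
|---|---|---|
| Change and percent change | missing | LLOQ/2 |
| Maximum decrease (built from change) | visit lost | LLOQ/2 |
| Absolute value, minimum value | missing for descriptive statistics | not stated |

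The LLOQ/2 rule in 4.2.2 is limited to change from Baseline, so the second route leaves absolute-value summaries and the minimum value open.

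**2. When BLQ values could arise**

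Inputs: the screening floor of 6 g/L (protocol 6.2.1) and an expected maximum mean reduction above 70% on three 7 mg/kg doses (protocol 5.4.2). A 70% fall from the floor gives 6 × (1 − 0.70) = 1.8 g/L. BLQ values become common only if the LLOQ is near or above that level. The LLOQ is not in the documents.

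**3. A small worked example (assumed figures)**

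Five subjects, each with Baseline 7 g/L; LLOQ 2 g/L; four results of 3.5, 2.8, 2.45 and 2.1 g/L, and one BLQ.

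- The four percent changes are -50, -60, -65 and -70.
- Missing rule: (-50 - 60 - 65 - 70)/4 = -61.3%.
- LLOQ/2 rule: the fifth value becomes 1.0 g/L, a change of 100 × (1 − 7)/7 = -85.7%. The mean is (-245 - 85.7)/5 = -66.1%.

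**4. Mean percent change across a range of LLOQ values (simulation, assumed inputs)**

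Baseline log-normal with median 10 g/L and log-SD 0.25, values below the entry limit raised to 6.01 g/L; percent reduction normal with mean 70 and SD 8 points; true mean change -70.0%.

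| LLOQ (g/L) | BLQ | Missing rule | LLOQ/2 rule |
|---|---|---|---|
| 0.3 | 0.0% | -70.0% | -70.0% |
| 1.0 | 1.0% | -69.8% | -70.0% |
| 1.5 | 5.1% | -69.2% | -70.3% |
| 2.0 | 16.0% | -68.1% | -71.2% |
| 2.5 | 33.1% | -66.7% | -72.7% |

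The missing rule understates the mean percent reduction wherever BLQ values occur. LLOQ/2 is closer to the truth in each such row but overshoots as the LLOQ rises. The mean IgG level behaves in the same way: at an LLOQ of 2.0 g/L the true mean is 3.10 g/L, against 3.38 under the missing rule and 3.00 under LLOQ/2.

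**5. Mean absolute change**

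The inputs are as in step 4, but baselines of 6 g/L or less are dropped rather than raised. At an LLOQ of 2.0 g/L:

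- Reduction SD 8 points: true -7.30 g/L; missing rule -7.36, an overstatement.
- Reduction SD 12 points: true -7.29 g/L; missing rule -7.12, an understatement.

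The direction for absolute change therefore depends on the spread of baselines and responses. LLOQ/2 gives -7.38 and -7.37 in the two cases. It is no closer than the missing rule in the first, and closer in the second.

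**The case against.** The strongest reply is that this is a contingency rule for values the SAP does not expect. With a low LLOQ nothing changes in any table, and total IgG is summarised only descriptively. That stands, and it is why the point is minor.

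Second, 4.2.3 is the dedicated section and names total IgG, whereas 4.2.2 is headed for safety laboratory data and 9.2 is a one-line generic reference, possibly a slip. On that reading 4.2.3 governs. This is plausible, but correcting only the reference would leave the weaker rule in force. A reader might also infer that the conflict was left so that a rule could be picked after the data are seen; nothing in the documents supports that.

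Third, LLOQ/2 is itself a convention, and it errs in the drug's favour when the LLOQ is high. The tables confirm this. It is a reason to report BLQ counts.

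Three stronger readings are tempting and fail:

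- **The missing rule makes a table more likely to be suppressed.** It does not. The limit ("Descriptive statistics will be calculated if at most 33% of the individual data points at a time" point are missing or not quantifiable) counts a BLQ value under either rule.
- **The bias always shrinks the effect.** That holds for percent change in the illustrations above, but step 5 shows both directions for absolute change.
- **A BLQ value marks the best response.** BLQ status depends on the level reached, so it also selects low baselines. With an LLOQ of 2 g/L, a 70% fall from 6.1 gives 1.83 g/L (BLQ), while an 80% fall from 12 gives 2.4 g/L (quantifiable).

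**Conclusion.** The inconsistency is real. As written, one BLQ total IgG value is missing under 4.2.3 and LLOQ/2 under 9.2, and neither route is complete for absolute values under an imputation rule. The missing rule is the poorer one, because it removes results for being low. It raises the mean level, understates the mean percent reduction, and can lose the nadir behind the minimum value and maximum decrease.

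The size runs from nil to a few percentage points: no difference at an LLOQ of 0.3 g/L, and 1.9 points too small a reduction (70.0 − 68.1) at 2.0 g/L. This rests on assumed baselines, responses and LLOQ values, since the documents state no LLOQ. Severity is minor. A secondary-objective pharmacodynamic summary is affected, and the primary QMG analysis is not.

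**What to change.** - In SAP 4.2.3, replace the missing rule for total IgG with LLOQ/2, as for the IgG subclasses. State that it applies to absolute-value summaries, minimum value, change, percent change and maximum decrease.
- In the same place, make the rule for values above the limit of quantification cover total IgG explicitly, so that redirecting 9.2 leaves no gap.
- In SAP 9.2, point the reference to 4.2.3 instead of 4.2.2.
- Report the number of BLQ total IgG values per visit and treatment group.

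The cost is a few sentences of text and one row in the total IgG table. The small downside is that LLOQ/2 slightly overstates the reduction if the LLOQ is high; the BLQ counts let a reader see when that could matter.

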As individual disease entities, IgG autoantibody mediated conditions are relatively rare. Treatment of these disorders remains a difficult clinical problem, requiring in many of these conditions the long-term use of high-dose corticosteroids alone or combined with cytotoxic agents. These therapeutic approaches are not effective in all patients and conditions and have broad immunosuppressive effects causing considerable toxicity and treatment-related morbidity. Treatments aimed at reducing the quantity of circulating IgG autoantibody, including plasmapheresis, immunoadsorption, or high-dose intravenous immunoglobulin (IVIg), are being used for primary and secondary therapy of autoimmune disease, particularly where atiations thereof corticosteroid-based immune suppression is not or no longer effective (eg, immune thrombocytopenic purpura [ITP], MG, and chronic inflammatory demyelinating polyradiculoneuropathy). The therapeutic approach of these treatments is thought to be based on lowering levels of pathogenic autoantibodies, which represents rational and effective treatment modalities of autoimmune diseases.

Myasthenia gravis is a rare autoimmune disorder of the peripheral motor system in which autoimmune antibodies most commonly form

at the neuromuscular junction (NMJ). The autoantibody impairs the ability of to bind to receptors, and leads to the destruction of receptors, either by inducing the muscle cell to eliminate the receptors through endocytosis or by complement fixation. A second category of MG is due to autoantibodies against the

which is required for the formation of the NMJ. Antibodies inhibit signaling, resulting in a decrease in patency of the NMJ, and the against consequent symptoms of MG. In both categories, this results in a characteristic pattern of progressively reduced muscle strength with repeated muscle use and muscle strength recovery following a period of rest. Additional antibodies have been found to be associated with MG but less is yet known about them and they appear less common than the main two. The essential role of the autoimmune antibodies in mediating this pathology is supported by the improvement seen after plasma exchange (PLEX). Plasma Exchange which reduces IgG levels including pathogenic IgG autoantibody is used both in patients non-responsive to

inhibitors or immunosuppressive treatments and in patients experiencing myasthenic crisis (Gilhus and Verschuuren, 2015).

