In summary, the genetic, epigenetic, and genomic elements of MG require further elucidation to understand the cause, progression, and appropriate treatment of MG. Through the voluntary collection of blood DNA and RNA samples from consenting subjects, this substudy will help enable further investigation of this complex disease. This documen

6

prior to

SELECTION AND WITHDRAWAL OF SUBJECTS

6.1 **Inclusion criteria**

To be eligible to participate in this study, all of the following criteria must be met:

- variations thereof 1. An Institutional Review Board (IRB)/Independent Ethics Committee (IEC) approved written Informed Consent form is signed and dated by the subject.
- 2. Subject is ≥ 18 years of age at Visit 1 (Screening).
- 3. Subject has a well-documented diagnosis of MG at Visit 1 (Screening), based on subject history and supported by previous evaluations. 5
- 4. Subject would currently be considered for treatment with immunological therapy (eg IVIG/PLEX) by the investigator.
- 5. Subject has a well-documented record of autoantibodies against or Visit 1 (Screening).
- 6. Female subjects of child bearing potential must have a negative serum pregnancy test at the Screening Visit, which is confirmed to be negative by urine testing prior to the first dose of study drug at Week 1 (Visit 2) and prior to further dosing at each study visit thereafter.

Female subjects of childbearing potential must agree to use a highly effective method of birth control, during the study and for a period 2 months after their final dose of study drug. According to the International Council for Harmonisation (ICH) M3 (R2), highly effective forms of birth control are methods which achieve a failure rate of less than 1% per year when used consistently and correctly. Highly effective methods of birth control include:

- Combined (estrogen- and progesterone-containing) hormonal contraception (oral, implant, injectable) associated with inhibition of ovulation, (which must be stable for at least 1 full month prior to Screening [Visit 1], and should remain stable during the study).
- Progesterone-only hormonal contraceptives (oral, implant, injectable) associated with inhibition of ovulation (which must be stable for at least 1 full month prior to Screening [Visit 1], and should remain stable during the study).
- Progesterone-releasing intrauterine systems or the TCu 380A intrauterine device.

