9.2.2 MG-specific autoantibodies

MG-specific autoantibodies [REDACTED] will be listed by treatment and time point including changes from Baseline and percentage changes from Baseline. Descriptive summaries (including n, arithmetic mean, median, SD, minimum and maximum) will be presented by treatment group and time point for absolute values, changes from Baseline and percentage changes from Baseline.

Mean and mean percentage change from Baseline values in MG-Specific autoantibodies will be plotted over time by treatment and period with all treatments overlaid on the same plot.

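### MG-specific autoantibody summaries are not limited to carriers: non-carriers dilute the mean, and the 33% rule usually removes the group statistics for an antibody carried by fewer than about two thirds of a group

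*SAP*

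**What the plan says.** **Who is admitted.** Inclusion criterion 5 (Protocol 6.1) reads "Subject has a well-documented record of autoantibodies against or", with the target names blacked out on either side of the conjunction. Carrying one antibody is therefore enough. The Protocol Introduction describes more than one antibody type: "A second category of MG is due to autoantibodies against the" a further target, also blacked out. It then says "Additional antibodies have been found to be associated with MG but less is yet known about them". No prevalence or overlap is given.

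**Who is summarised.** SAP 9.2.2 gives descriptive summaries of levels, changes and percentage changes by treatment group and time point, and adds "Mean and mean percentage change from Baseline values in MG-Specific autoantibodies will be plotted over time by treatment and period". SAP 9.2 first states "The analysis of the PD data will be performed on the FAS with the exception of the total serum IgG and IgG subclasses results", then says that everything in the section uses the PD-PPS. Neither set refers to which antibody a subject carries, and SAP 4.9 plans no subgroups. SAP 9.2.2 also lists every subject's autoantibody values with changes and percentage changes.

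**How unquantifiable values are treated.** SAP 4.2.3 says "For the MG-specific autoantibodies and IgG subclasses, measurements BLQ will be imputed with LLOQ/2 for the purpose of calculating change from Baseline". It also sets the display condition, "Descriptive statistics will be calculated if at most 33% of the individual data points at a time point are missing", where values below LLOQ or above the upper limit count together with missing ones. The autoantibodies are not exempted.

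**The concern.** A display rule suited to poor assay yield is here applied to subjects who may simply not have the antibody. A subject below LLOQ at Baseline and afterwards has a change of LLOQ/2 minus LLOQ/2, which is zero whatever the drug does. The reported mean then mixes the drug effect with the share of carriers, and small groups can differ because of chance in serotype. When non-carriers pass 33% of a group, the statistics disappear even if every carrier responds.

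The same limit also counts carriers whose level falls below LLOQ on treatment, so the summary is likeliest to be lost where the drug works best.

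The output at stake is the group description of the effect on MG-specific autoantibodies. This is an exploratory objective and a named PD variable in a study of a drug meant to lower pathogenic IgG.

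**Working it through.** The plan states no figure to reproduce here.

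**Inputs**
- Display limit of 33% and LLOQ/2 substitution: SAP 4.2.3.
- Group sizes: about 42 randomised and 40 evaluable (SAP 2.3), so about 20 to 21 per arm in Dosing Period 1 and about 10 per treatment sequence afterwards.
- Fall in carriers: 70%, an assumption. It is borrowed from the total-IgG planning figure in Protocol 5.4.2, because no autoantibody figure is given.
- Carrier share p: not in the documents, so shown as a range.
- Non-carriers read below LLOQ and carriers are quantifiable: an assumption.

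**Step 1: unquantifiable or missing values allowed.** The largest k with k/n ≤ 0.33 is 6 for n = 20 (30.0%), 6 for n = 21 (28.6%; 7/21 = 33.3% is already over) and 3 for n = 10 (30.0%).

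**Step 2: chance that statistics are shown, and the expected mean.** P(shown) = P(Bin(n, 1 − p) ≤ k). Expected mean percentage change = p × (−70%), since non-carriers contribute 0%.

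| Carrier share p | Shown, n = 20 | Shown, n = 10 | Expected mean |
|---|---|---|---|
| 95% | about 100% | 99.9% | −66.5% |
| 90% | 99.8% | 98.7% | −63.0% |
| 85% | 97.8% | 95.0% | −59.5% |
| 80% | 91.3% | 87.9% | −56.0% |
| 70% | 60.8% | 65.0% | −49.0% |
| 60% | 25.0% | 38.2% | (−42.0%) |
| 50% | 5.8% | 17.2% | (−35.0%) |
| 30% | 0.03% | 1.1% | (−21.0%) |
| 15% | about 0 | 0.01% | (−10.5%) |

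Means in brackets belong to tables that would usually not be shown.

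**Step 3: worst dilution while still shown.** With 6 non-carriers of 20, the mean is 14/20 × (−70%) = −49%. With 3 of 10 it is 7/10 × (−70%) = −49%. With 6 of 21 it is 15/21 × (−70%) = −50%. The loss is 30%, 30% and 28.6% of the effect. If all carriers fall by 70%, the median is −70% in each case.

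**Step 4: chance differences between sequences.** One sequence of 10 with no non-carriers would show −70% and another with three would show −49%. That 21-point gap comes from serotype alone.

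**Step 5: two antibodies together.** If hardly anyone carries both, the shares sum to at most about 100%, so both cannot reach 67%. The rarer one is then at 50% or less and is shown in at most 5.8% of arms of 20. With a 60/40 split, the chances for an arm of 20 are 25.0% and 0.65%.

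**Step 6: treatment effect counted against the limit.** In an arm of 20 with 17 carriers and 3 non-carriers, four carriers falling below LLOQ give 7/20 = 35%, and the statistics are dropped.

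**The case against.** A reader might infer that the rarer antibody's result is never reported. The documents do not support that. SAP 9.2.2 lists every subject's values, changes and percentage changes, and the 33% rule governs descriptive statistics only. What is lost is the group table and, on a natural reading, the mean plots.

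A reader might also infer heavy dilution together with suppression. The two do not occur in the same table: the rule that removes a summary also caps the dilution of any summary shown. If one antibody dominates, its mean is only slightly diluted. SAP 9.2.2 already plans the median, which a minority of zeros hardly moves.

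Other objections carry weight:
- An "Subject has a well-documented record of autoantibodies against or" criterion does not exclude carrying both antibodies, and a seronegative sample need not read below LLOQ. Carrier shares, overlap and assay limits are not in the documents.
- Words are blacked out in SAP 9.2.2. They stand where antibody names would be, but a restriction hidden there cannot be wholly excluded.
- The schedule of assessments puts no serotype condition on autoantibody sampling. It is therefore speculative that the second antibody would go unassayed in non-carriers and count as missing.
- For a rare antibody the gain from restricting to carriers is small. At 10% carriers, an arm of 20 has about 2 and a sequence of 10 about 1. Under SAP 3.1, fewer than 3 subjects get only n, minimum and maximum.

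None of this supplies a carrier restriction or exempts the autoantibodies from the limit. The mechanism stands and its reach is narrower.

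**Conclusion.** The concern holds in a bounded form. As written, the SAP summarises the autoantibodies in subjects who need not carry them. If non-carriers read below LLOQ, a displayed mean is diluted in proportion to their share, by at most about 30% of the effect and by 5 to 10% when 90 to 95% are carriers. The median is little affected. For an antibody carried by fewer than about two thirds of a group, group statistics are usually not produced and only the listing remains. The commoner antibody is exposed too: at 70% carriers an arm of 20 loses its statistics about 39% of the time (100% − 60.8%), before counting missing samples or carriers pushed below LLOQ.

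These sizes rest on assumed carrier shares, on non-carriers reading below LLOQ and, for the means, on a 70% fall borrowed from total IgG. The consequence is confined to descriptive output for an exploratory objective. The primary and secondary efficacy analyses are unaffected.

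**What to change.** - **SAP 9.2.2:** summarise and plot each autoantibody in subjects quantifiable for it at Baseline, with n shown at each time point. Apply LLOQ/2 to their later values below LLOQ. Keep all subjects in the listing.
- **SAP 4.2.3:** do not let values below LLOQ in this set suppress the autoantibody summary. Report the median and the number below LLOQ beside the mean.
- **SAP 9.2:** in the same edit, settle whether the autoantibodies are analysed on the FAS or the PD-PPS, since the section names both.

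The cost is SAP wording and one Baseline flag per antibody; no new samples or visits are needed. The downside is small cells for a rarer antibody, where the rule in SAP 3.1 for fewer than 3 subjects will still limit the display to n, minimum and maximum.
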